6. GENERAL STATISTICAL CONSIDERATIONS

6.1. Interim Analysis and Data Monitoring

One or more Interim Analysis (IA) may be conducted. The first IA will assess number of responders in Stage 1 (first 11 participants). Data may be monitored on ongoing basis which will include monitoring of enrollment of population sub-groups.

6.2. Multi-Center Studies

This is a multi-center study. Given the small sample size of the study, no site effect will be considered in primary or secondary statistical analysis. Site or geography impact may be considered in the exploratory analysis if deemed appropriate.

6.3. Multiple Comparisons

No adjustment of P -values for multiple comparisons will be conducted.

6.4. Handling of Dropouts or Missing Data

The primary analysis will be based on the observed available data – no data imputations will be conducted. For the survival analysis, dropouts without confirming events will be treated as censored.

As part of the exploratory analysis, sensitivity analysis using appropriate data imputation models may be conducted. The impact of different imputation models will be assessed and compared to main analysis.

7. SUMMARY OF STUDY POPULATION DATA

7.1. Subject Disposition

Subject disposition will be provided for all subjects screened. The disposition table will include the total number of subjects screened, total number of screen failures, and total number who received any study drug will be displayed. Among subjects who received any study drug, frequency and percentage of subjects who completed treatment, prematurely discontinued and reasons for premature discontinuation and reason for end of study will be tabulated. Subjects will be presented throughout by their genetic subtype: AITL, PTCL, CXCL12+, and an Other category, which includes one subject that is ALCL-ALK negative and one that is PTCL sub-type not otherwise specified in the protocol.

Detailed subject disposition information, subject eligibility, and analysis population assignment will be displayed in separate listings.

7.2. Protocol Deviations

All protocol deviations will be documented and classified (minor, major, critical) prior to study data base lock. Listing and appropriate summary tables of all protocol deviations will be produced as part of the final analysis.

7.3. Demographics and Baseline Characteristics

Descriptive statistics will be provided for subject demographics and baseline characteristics. The following summary tables will be provided:

- Demographics and baseline characteristics at screening to include age and sex.
- Ethnicity and race will be stated where allowed by local regulatory authorities. Measurements of height, weight, and ECOG performance status score will be summarized for the ASaT, FAS, [REDACTED] Populations.
- Medical and surgical history/physical findings will be coded using Medical Dictionary for Regulatory Activities (MedDRA) version 19.0 and summarized by system organ class (SOC)/preferred term (PT) for the ASaT population.
- Cancer history at screening will be summarized by diagnosis and stage for the ASaT population.
- Prior anti-cancer therapy, cancer surgery and radiation therapy will be summarized for the ASaT population and for the FAS population. For prior anti-cancer therapy, descriptive statistics on the number of regimens per subject and best overall response on last prior therapy will be presented.
- Last therapy progression free survival will be presented. Progression free survival on last prior therapy will be calculated as follows:

$([\text{Progression Date} - \text{Earliest Treatment Initiation Date of Most Recent Prior Cancer Therapy}] + 1)/30.4375$. If date of progression is not available for the last prior therapy, then the start date of Tipifarnib will be used to calculate PFS.

- Kaplan Meier curves will present a comparison PFS on last prior therapy for the ASaT population by cohort compared to PFS on tipifarnib using a Cox Proportional Hazards model.

The following listings will be provided:

- Subject demographics
- Baseline medical, surgical history/physical findings
- Biopsy sample at screening
- Buccal swab sample at screening
- Cancer history at screening

- Previous anti-cancer therapy
- Prior cancer surgery
- Prior radiation therapy
- Disease related symptom assessment at screening
- Prior stem cell transplants at screening
- ECOG performance status

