3.5. Randomization and Blinding

This is a single arm open label study. There is no randomization or blinding involved in this study.

[figure not shown]

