4. SAMPLE SIZE CONSIDERATIONS

The study can enroll up to 70 participants. A multi-stage study design, which potentially assumes enrollment of the patients in three consecutive groups (11, 7, and up to 52 participants) will be employed. This design is intended to allow for the termination of accrual in case of unacceptably low efficacy. The objective responses will be evaluated in the first 11 participants (Stage 1) assessed in a Full Analysis Set (FAS). If 0-1 objective responses are observed after the first 11 evaluable subjects, the study will be closed to further enrollment. If 2-4 responses are observed, 7 additional subjects will be enrolled (Stage 2). Treatment will be considered of further interest (successfully passing Stage 2 to full enrollment) if at least 4 responses are observed (out of 18 subjects) in Stage 2.

In order to assess the operating characteristics of the design the following assumptions are made:

- Null hypothesis of ORR = 10% is tested using a two-sided binomial test (based normal approximation) with significance level $\alpha \leq 0.05$.
- All participants, despite population heterogeneity in terms of sub-types, have the same true ORR.
- Study total sample size is 65 evaluable participants given successful transition from stages 1 and 2 to full enrollment.

[figure not shown]
[Figure 1](#) depicts the relationship between the true ORR and power (red line) – probability of rejecting the null hypothesis given the assumptions above. It also shows the likelihood of passing Stage 1 (blue line) and Stage 2 (green line). When the true ORR is 30%, the probability of passing Stage 2 and rejecting the null hypothesis at the end of the study ($N = 65$) is approximately 80%. These probabilities are increasing to approximately 99% when the true ORR is 50%. For ORR = 10%, the probability of passing Stage 1 is 30% (and 8% to pass Stage 2).

Figure 1: Operating Characteristics of Study Design

Further sample size considerations are related to assessment of ORR in the subgroup of participants with AITL (N = 12) and CXCL12 (N = 12) subtypes. Figure 2 visualizes a 95% two-sided confidence interval for a hypothetical observed number of responders in the cohort consisting of 12 participants. It should be noted that the method of evaluating the confidence interval changes from Wilson¹ to Pearson-Clopper² if the number of responders falls below three.

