8.2. Secondary Efficacy Analysis

The secondary efficacy analysis will focus on DOR and PFS analysis in the study population (FAS analysis data set), as well as on subgroup analysis of ORR, PFS, and DOR in genetic sub-types (AITL, PTCL-NOS, CXCL12+, and Other).

The duration of the response will be calculated for subjects who achieve an objective response (either CR or PR, whichever comes first). For such subjects, the duration of the objective response is defined as the number of days from the start date of the objective response to the first date of either documented progressive disease or death. All efforts will be made to objectively define the endpoint by collecting the necessary data and reducing the likelihood of missing data. In the event of a maintained response, the DOR will be censored at the last evaluable non-PD assessment.

Disease progression will be determined by the investigator using the primary efficacy endpoint assessment. Progression free survival will be defined as the time (in months) from first dose (Cycle 1 Day 1) to the minimum date of progression or death, if death occurred within 126 days

³ Wilson, E. B. (1927). "Probable inference, the law of succession, and statistical inference". *Journal of the American Statistical Association*. 22 (158): 209–212.

⁴ Clopper, C.; Pearson, E. S. (1934). "The use of confidence or fiducial limits illustrated in the case of the binomial". *Biometrika*. 26 (4): 404–413.

of the last treatment or assessment. If the subject goes off study with no documentation of PD, the censoring date will be the date of the last evaluable assessment.

Sensitivity analyses may be conducted to explore the effect of different censoring on DOR and PFS.

The duration of the objective response and progression free survival will be analyzed using the Kaplan-Meier (KM) method. 95% CI for KM curve will be constructed using Greenwood's⁵ formula in the log-log scale.

The median DOR and PFS will be evaluated using the 50th percentile of KM distribution. 95% CIs for the median will be constructed based on a robust nonparametric method of Brookmeyer and Crowley⁶.

Summary tables and advanced data visualizations will be used for presenting KM plots, 95% CIs for probabilities of surviving X months, and a median survival estimate with its 95% CIs. The analysis will be conducted on FAS (primary) [REDACTED] populations.

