12. DATA HANDLING CONVENTIONS

Analyses will be performed using SAS® [SAS Institute 2011] Version 9.3 or higher.

The clinical database will be locked prior to the initiation of the final statistical analyses. A database lock is defined as a stable database that can be analyzed and reported. Changes to a locked database must be authorized in writing by the study sponsor and [REDACTED] standard operating procedures (SOPs).

The data conventions include the following.

- Data will be described and summarized by cohort, according to Protocol Amendment version.
- Summary tables for continuous variables will contain the following statistics: N (number of subjects in the population); n (number of subjects with data for that variable); mean; standard deviation; median; minimum; and maximum. Selected statistics may also include 2 sided 95% normal approximation confidence intervals (CI) on the mean.
- Summary tables for categorical variables will include: N (number of subjects in the denominator); n (number of subjects in the numerator); and percent. Selected statistics also may include a 2-sided 95% CI.
- The baseline value for a given parameter is the last value prior to the first dose. A value is considered to be post-baseline if it is obtained after the first dose. A value is considered to be post-dose on a given cycle day if it is obtained after the dose is administered on that day.
- Data from all study centers will be pooled for all analyses.

- Unless otherwise specified, statistical testing will be 2-sided at a nominal 0.05 level of significance.
- Study day is defined as calendar date – date of first treatment + 1 if the calendar date is on or after the date of first treatment, and calendar date – date of first treatment if the calendar date is before the date of first treatment
- Missing data conventions for individual endpoints are described in the SAP section for the endpoint.
- Listings will be provided for all data collected in the eCRF.

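### The Cox comparison of PFS on last prior therapy with PFS on tipifarnib makes no stated allowance for pairing, and the missing-date rule lengthens prior PFS without saying whether the substituted time is an event

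*SAP*

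**What the plan says.** SAP Section 7.3 (Demographics and Baseline Characteristics) contains the whole plan for this comparison.

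- **The comparison.** "Kaplan Meier curves will present a comparison PFS on last prior therapy for the ASaT population by cohort compared to PFS on tipifarnib". The end of the same sentence names the model: "compared to PFS on tipifarnib using a Cox Proportional Hazards model". No strata, frailty, clustering or robust variance is mentioned here or elsewhere for this analysis.
- **The pairing.** SAP Section 3.5: "This is a single arm open label study". Both times therefore come from the same people.
- **Prior PFS.** It runs from the start of the most recent prior therapy to its progression date, in months. "If date of progression is not available for the last prior therapy, then the start date of Tipifarnib will be used to calculate PFS". The event status of that time is not stated.
- **PFS on tipifarnib.** SAP Section 8.2: "Progression free survival will be defined as the time (in months) from first dose (Cycle 1 Day 1) to the minimum date of progression" or qualifying death, and otherwise censored.
- **Testing.** SAP Section 12 sets the default: "Unless otherwise specified, statistical testing will be 2-sided at a nominal 0.05 level of significance". SAP Section 6.3 adds: "No adjustment of P -values for multiple comparisons will be conducted".

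The optional sensitivity analyses on censoring in SAP Section 8.2 concern PFS and DOR on study. None is named for PFS on last prior therapy.

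**The concern.** There are two separate problems.

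First, a Cox fit with its usual model-based variance treats the two records of one subject as independent. If they are correlated, the standard error does not describe the real sampling variation of the log hazard ratio. The interval is then too wide when the correlation is positive and too narrow when it is negative.

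Second, for a subject who progressed on the last therapy before starting tipifarnib, the substituted date is later than the true one. Prior PFS is lengthened and tipifarnib looks worse by comparison. Missing dates are foreseeable: the SAP has a rule for them. Protocol Table 1 (footnote 17) asks for response and its duration on the last prior therapy but does not name a progression date, and Protocol Section 8.1 promises only efforts to collect that information.

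ORR is tested against a fixed 10%, so this is the only planned comparison of tipifarnib with observed outcomes on another treatment. Readers will look at it, and any p-value falls under the nominal 0.05 default.

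**Working it through.** The documents give no hazard ratio, standard error, event count or power for this comparison, so there is no planned figure to reproduce.

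**Inputs from the documents.** 65 evaluable subjects (SAP Section 4); AITL and CXCL12+ cohorts of 12 each in the same section (the AITL cohort was later extended by up to 20); two-sided 0.05.

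**Assumptions, not in the documents.** Exponential times; median prior PFS 4 months; tipifarnib PFS censored uniformly between 3 and 24 months; within-subject correlation ρ (Gaussian copula) from −0.3 to 0.6; 10% to 40% of prior progression dates missing; mean gap from true progression to tipifarnib start 1 to 3 months. Each setting used 1,500 to 3,000 simulated trials.

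**Step 1: size of the model-based standard error.** It is roughly √(1/d₁ + 1/d₂), with d₁ and d₂ the event counts. All 65 prior times are events. With rate λ = ln 2/4 = 0.1733 per month, the expected event fraction on tipifarnib is 1 − (e^(−3λ) − e^(−24λ))/(21λ) = 0.841, or 54.7 events. So SE ≈ √(1/65 + 1/54.7) = 0.184. The simulated value is 0.188. The formula contains no ρ, and the simulated SE does not move with ρ.

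**Step 2: effect of pairing, 65 pairs, true HR 1.** If the ratio r is model SE divided by true SD, the real type I error is about 2[1 − Φ(1.96 r)].

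| ρ | True SD of log HR | Model SE | Clustered SE | r | Type I, formula | Type I, simulated | Type I, clustered |
|---|---|---|---|---|---|---|---|
| −0.3 | 0.206 | 0.188 | 0.207 | 0.91 | 0.074 | 0.068 | 0.045 |
| 0 | 0.193 | 0.188 | 0.186 | 0.97 | 0.056 | 0.053 | 0.057 |
| 0.3 | 0.160 | 0.188 | 0.161 | 1.17 | 0.021 | 0.019 | 0.045 |
| 0.6 | 0.130 | 0.187 | 0.129 | 1.44 | 0.005 | 0.005 | 0.054 |

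The mean HR stays at 1.00 for every ρ, so pairing alone does not bias it. At a true HR of 0.70, power without and with clustering is 44% and 58% at ρ = 0.3, and 44% and 76% at ρ = 0.6.

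**Step 3: the date rule.** For exponential times the rate is events divided by total time, and mean prior PFS is 4/ln 2 = 5.77 months. If a fraction f of dates is missing and each is moved later by g months on average:

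- substituted time counted as an event: HR′ = HR × (1 + f·g/5.77)
- substituted time counted as censored: HR′ = HR × (1 + f·g/5.77)/(1 − f)

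Worked case, f = 0.4, g = 3, true HR 0.70: 0.70 × (1 + 1.2/5.77) = 0.846 as events, and 0.846/0.6 = 1.41 as censored. The simulation gives 0.86 and 1.39. The full simulated grid at true HR 0.70 and ρ = 0.3, with gaps of 1 and 3 months:

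| Dates missing | As event | As censored |
|---|---|---|
| 0% | 0.70 | 0.70 |
| 10% | 0.71, 0.73 | 0.79, 0.82 |
| 20% | 0.73, 0.78 | 0.91, 0.95 |
| 40% | 0.75, 0.86 | 1.26, 1.39 |

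The unstated event status matters more than the gap. At 40% missing, two analysts following the same SAP could report hazard ratios on opposite sides of 1. The text supports either reading: the formula in Section 7.3 puts the date in the place of a progression date, while SAP Section 6.4 treats dropouts without a confirmed event as censored in survival analyses.

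**Step 4: cohort size.** With 12 pairs and true HR 1, the clustered test has type I error 0.080, 0.079 and 0.072 at ρ = 0, 0.3 and 0.6. The clustered SE is itself too small (0.380 against a true SD of 0.422 at ρ = 0.3).

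**The case against.** The strongest reply is that the SAP names a Cox model and stops there. A reader might infer that it chose an independent-samples analysis, but silence is not a choice, and a programmer could add clustering without breaking the plan. This stands as a point about wording; it is also why the SAP should say which variance it means.

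A reader might also infer that the interval and the hazard ratio are both wrong. The documents do not support that. The marginal hazard ratio is unaffected by pairing, the standard error is about right at zero correlation, and the date rule does nothing if no dates are missing. Neither the correlation nor the missing fraction is given.

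It is tempting, too, to say that true progression must always precede the substituted date. Inclusion criterion 3 (Protocol Section 7.1) requires failure of at least one prior cytotoxic therapy, not of the last one. Someone who stopped the last therapy without progressing has no earlier event to find. That objection stands, and such subjects need their own rule.

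Finally, the comparison is listed among baseline summaries. It is not a stated objective and has no hypothesis, power or decision rule. With positive correlation both errors work against tipifarnib, so they would not create a false claim of benefit. This stands and limits the importance of the point. SAP Section 8.2 does call sensitivity analysis critical for the main subgroup analyses, but it does not name this comparison.

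**Conclusion.** The point holds as a cheap improvement to a descriptive analysis. Followed as written with a model-based variance, the Cox interval is miscalibrated whenever the two times are correlated. For ρ of 0.3 to 0.6 and 65 pairs the standard error is about 17% to 44% too large, and real type I error is 0.019 to 0.005 instead of 0.05. The date rule lengthens prior PFS for anyone who progressed before tipifarnib. It moves an assumed true hazard ratio of 0.70 to about 0.71–0.86 if substituted times are events and 0.79–1.39 if they are censored, over 10% to 40% missing and gaps of 1 to 3 months.

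Correlation, median, censoring, missing fraction and gap are all assumptions. The directions are firmer than the sizes: the date rule can only lengthen prior PFS for those subjects, and the sign of the interval error follows the sign of the correlation. No trial decision depends on this result.

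**What to change.** Amend SAP Section 7.3 as follows.

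1. Fit the pooled Cox comparison with robust variance clustered on subject (marginal hazard ratio), or stratify by subject (within-subject hazard ratio), and say which.
2. Do not use the tipifarnib start date as an exact event time in the main comparison. For subjects known to have progressed on the last therapy, treat the time as interval-censored from the last known progression-free date up to tipifarnib start, or exclude the pair. For subjects who stopped that therapy without progressing, censor at the last known progression-free date.
3. Report how many dates are affected, by cohort. Show the substitution only as a sensitivity analysis, with its event status stated.
4. In cohorts of about 12, show paired times or within-subject PFS ratios descriptively, because the clustered standard error is too small there.

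**Cost.** Clustering or stratification is one procedure option. Interval-censoring needs a different model and so some extra programming; excluding the pairs is the simpler alternative. A few pairs will carry less information. No new data collection is needed beyond recording whether the subject progressed on the last therapy and when the subject was last known to be progression-free, where the site has this.

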7.4. Dosing and Extent of Exposure

Number of treatment cycles and average dose intensity per treatment cycle will be summarized using descriptive statistics. Total incidences of drug modification (dose reduction, dose interruption, dose increase, or drug withdrawn), frequency and percentage of subjects who experienced drug modification, and summary statistics of number of drug modifications per subject will also be summarized.

Per subject log of study drug number of pills returned and dispensed will be displayed in a listing; tipifarnib dosing log will also be displayed in a listing.

7.5. Concomitant Medications

Prior and concomitant medications (other than cancer treatment) will be coded by World Health Organization Drug Dictionary (WHODRUG) version Dec-2015 B2 and summarized by preferred Anatomical Therapeutic Chemical 3 terms and preferred terms. Prior cancer-treatment medications will be similarly summarized.

Prior and concomitant medication (other than cancer treatment) will be displayed in a listing.

Non-drug treatments or procedures will also be listed.

7.6. Follow Up Assessments

Information on subsequent therapy and survival from follow up contacts will be displayed in separate listings.

8. EFFICACY ANALYSIS

8.1. Primary Efficacy Analysis

The primary endpoint will be based on response assessments according to the Lugano Classification (Protocol Appendix II). Either complete or partial responses can contribute to an objective response. The objective response rate, \hat{p}_{ORR} , will be estimated as a ratio of subjects with an objective response to the number of subjects (N) in the FAS data set.

The 95% Confidence Interval for ORR will be calculated using Wilson³ approximation.

If $\hat{P}_{ORR} \times N \leq 4$, the exact Clopper-Pearson⁴ method will be used for interval estimation.

Null hypothesis $H_0: \hat{P}_{ORR} = 10\%$ versus $H_A: \hat{P}_{ORR} > 10\%$ will be tested at $\alpha = 0.05$ significance level using a two-sided binomial test. The choice of test statistics will be driven by the method used for interval estimation.

The ORR analysis will be presented by means of a summary table and visualization. A summary table of the objective response rates will be provided for the primary efficacy endpoint for both the FAS [REDACTED] populations. [REDACTED]

The ORR will also be analyzed by study population subgroups (part of the secondary analysis) which are based on the genetic sub-types.

Sensitivity analysis, as part of the exploratory analysis, may also include analysis using different statistical approaches (different methods for interval estimation variants of normal approximation, Agresti-Coull, Pearson-Clopper, etc.), one-sided confidence intervals, test statistics, or a modelling framework). Exploratory analyses may also include a logistic regression modeling framework to evaluate the effect of genetic sub-types and other covariates on ORR.

Additional sensitivity and subgroup analysis, as part of exploratory analysis, may be conducted as deemed appropriate.

